CRA	Clinical Research Assistant / Associate
CRO	Clinical Research Organization
CTCAE	Common Terminology Criteria for Adverse Events
DSMB	Data Safety Monitoring Board
eCRF	Electronic Case Report Form
EDC	Electronic Data Capture
FDA	Food & Drug Administration
GCP	Good Clinical Practices
GMP	Good Manufacturing Practices
HREC	Human Research Ethics Committee
IB	Investigator's Brochure
IND	Investigational New Drug
IGA	Investigator's Global Assessment
IFN	Interferon
IL	Interleukin
IRB	Institutional Review Board
ITF	Investigator's Trial File
IVRS	Interactive Voice Response System
IWRS	Interactive Web-based Response System
MCH	Mean Corpuscular Haemoglobin
MCHC	Mean Corpuscular Haemoglobin Concentration
MCV	Mean Corpuscular Volume
MedDRA	Medical Dictionary for Regulatory Activities
NCI	National Cancer Institute
NSAID	Non-Steroidal Anti-Inflammatory Drug
OTC	Over the Counter
PK	Pharmacokinetics
p.m.	Post Meridiem
PPG	Polypropyleneglycol
PPP	Pharmaceutical Packaging Professionals

QA	Quality Assurance
QC	Quality Control
QD	Once Daily
RBC	Red Blood Cell
SAE	Serious Adverse Event
SAP	Statistical Analysis Plan
SAS	Statistical Analysis System
SD	Standard Deviation
SOP	Standard Operating Procedure
TEAE	Treatment Emergent Adverse Event
THC	Tetrahydrocannabinol
TMF	Trial Master File
UDS	Urine Drug Screen
UPT	Urine Pregnancy Test
vIGA-AD	Validated Investigator Global Assessment scale for Atopic Dermatitis
WBC	White Blood Cell
WHO	World Health Organization
WOCBP	Women of Child-Bearing Potential

PROTOCOL SUMMARY

Title:	A Randomized, Double-Blind, Vehicle-Controlled Study of the Safety, Tolerability and Efficacy of BTX 1204 in Patients with Moderate Atopic Dermatitis
Study Phase:	2a
Dose and Treatment Duration:	There will be two dose groups. All subjects will apply study drug for 84 days. 
 • BTX 1204 4% twice daily (BID), or • Vehicle BID
Study Duration:	There will be a total of up to 112 days; screening period (up to 28 days), and 84 days of treatment.
Investigational Product:	BTX 1204 Liquid Formulation
Concurrent Control:	BTX 1204 Vehicle
Administration Route and Form:	BTX 1204 4% (w/w) or Vehicle applied topically
Objective:	To determine the safety, tolerability and efficacy of BTX 1204 in subjects 12 to 70 years of age with moderate atopic dermatitis (AD).
Study Design:	This is a multi-center, randomized, double-blind, vehicle-controlled, parallel-group study.
Outcome Measures:	The efficacy of BTX 1204 4% (w/w) will be evaluated using the Validated Investigator Global Assessment scale for Atopic Dermatitis (vIGA-AD TM ; heretofore – IGA), Body Surface Area (BSA) of AD, Signs of AD (erythema, exudation, excoriation, induration/papulation, and lichenification), and Eczema Area Severity Index (EASI) Scores completed by the treating dermatologist along with Itching-Numerical Rating Score (I-NRS) and Worst Itching NRS (WI-NRS) scores reported by subjects. At selected sites, a target lesion will be identified, photographed and scored with the Signs of AD.

	
The efficacy outcome measures are:
 
Primary endpoint:
 
The primary efficacy endpoint for the study is the proportion of subjects with IGA success defined as an IGA score of “Clear” (0) or “Almost Clear” (1) with at least a 2-grade improvement from Baseline at Day 85.
 
Secondary endpoints:
 
The secondary endpoints for the study are:
 
 • The proportion of subjects with an EASI 75 score at Day 85, • The proportion of subjects with an EASI 50 score at Day 85, • The change from Baseline in the Signs of AD score at Day 85, • The proportion of subjects with an IGA of Clear or Almost Clear at Day 85, • The proportion of subjects with at least a 2-grade improvement in ISGA from Baseline at Day 85, • The change from Baseline in the percent of BSA affected by AD at Day 85, • The time to achieve IGA success, and • The change from Baseline to Day 85 in the I-NRS 
Exploratory endpoints:
 
The exploratory endpoints are:
 
 • The change from Baseline in the Signs of AD score at Day 15, Day 29, and Day 57, • The change from Baseline in the percent of BSA affected by AD at Day 15, Day 29, and Day 57, • The proportion of subjects with IGA success defined as an IGA score of “Clear” (0) or “Almost Clear” (1) with at least a 2-grade improvement from Baseline at Day 15, Day 29, and Day 57, • The percent change from Baseline in the EASI Score at Day 85,
--	---

	
 • Change from Baseline in the subject’s reports of pruritus obtained daily on a Patient Diary. • Time to improvement of pruritus (change of ≥ 4 in the Worst Itch Numerical Rating Score [WI-NRS, 0 – 10 score]), • Subject’s assessment of the change in their AD from Baseline to Day 85 (Patient Reported Outcome [PRO]), and • The change from Baseline to Day 29, and Day 57, and Day 85 in the Signs of AD score for the target lesion (at selected sites only). 
The safety outcome measures to be assessed are:
 
 • Reported adverse events (AEs) including treatment-emergent (TEAE) monitored from time of consent through the end of study; • Changes in clinical labs including complete blood count (CBC), chemistry, and urinalysis between Baseline and Day 85, • Subject’s reports of burning/stinging obtained during visits on Day 1, Day 15, Day 29, Day 57, and Day 85. 
Pregnancy testing will be conducted for women of child-bearing potential (WOCBP) at the Screening Visit, the Baseline Visit (if > 7 days from Screening Visit) and at the Day 29, Day 57 and Day 85 Visits.

Total Sample Size:	Approximately 200 subjects randomized 1:1 (100 subjects to BTX 1204 4% and 100 subjects to Vehicle) will be enrolled.
Methods:	
Subjects will begin screening to determine eligibility to participate in the study. Informed consent/assent, medical history/review of systems, demographics, height and weight will be obtained. Urine pregnancy testing (UPT) will be conducted for WOCBP and a urine drug screen (UDS) will occur. Measurement of the total body surface area (BSA) of AD involvement and IGA will be assessed at Screening. At selected photography sites, a target lesion will be identified.
 
Within 28 days after the Screening Visit, Baseline assessments for safety (CBC, chemistry, and urinalysis) will be obtained on Day 1. If the subject is eligible to participate, Screening and Baseline may occur at the same visit. If the Screening Visit and Baseline Visit are not concurrent, IGA, UPT, UDS, and BSA of AD, will be repeated at the

Baseline Visit. Review of eligibility criteria will be repeated. Signs of AD and the EASI scores will be obtained. Subjects will be asked to rate their pruritus using the itch numeric rating score (I-NRS) which is an average level of itch over the past 24 hours on a scale of 0 (no itch) to 10 (worst imaginable itch). At selected sites, photographs and Signs of AD scoring of the target lesion will be obtained. Subjects will be randomized 1:1 using an Interactive Web-based Response System (IWRS) to receive active BTX 1204 4% or Vehicle. Subjects will receive their first dose of study drug applied by the site staff and will be observed in the clinic for approximately 15 minutes after the initial application. Subjects will be given 4 weeks of study drug and instructed in the proper application for twice daily (BID) applications to cover their AD lesions, except on the scalp and groin.

Subjects will be provided with a diary to record their daily pruritus score using the worst itch numeric rating score (WI-NRS). Subjects will record the WI-NRS over the past 24 hours each day prior to their morning application. Subject will also record on the diary the time of their morning and evening applications of study drug.

Subjects will return to the clinic on Day 15. Subjects will be queried for adverse events and changes in concomitant medications since their previous visit. Returned study drug will be weighed and diaries will be reviewed for compliance. The site will obtain IGA, BSA of AD, Signs of AD score, EASI score. Subjects will be asked to rate their pruritus using the I-NRS. The subject will then apply their dose of study drug during the visit for the clinical site to confirm correct application techniques.

Subjects will return to the clinic on Day 29 and Day 57. Subjects will be queried for adverse events and changes in concomitant medications since their previous visit. A UPT will be done on WOCBP. Returned study drug will be weighed and diaries will be reviewed for compliance. The site will obtain IGA, BSA of AD, Signs of AD, and EASI Score. Subjects will be asked to rate their pruritus using the I-NRS. At selected sites, the target lesion will be photographed and scored with the Signs of AD score. The subject will then apply their dose of study drug during the visit for the clinical site to confirm correct application techniques. Another four weeks of study drug will be dispensed along with a new diary.

	
The final study drug application will be applied in the evening prior to the Day 85 Visit.
 
Subjects will return to the clinic for their final visit on Day 85 for safety assessments; blood samples for CBC and chemistry, and urine samples for urinalysis. A UPT will be conducted for WOCBP. Subjects will be queried for adverse events and changes in concomitant medications since their previous visit. Returned study drug will be weighed and diaries will be reviewed for compliance. The site will obtain IGA, BSA of AD, Signs of AD score, and EASI Score. Subjects will be asked to rate their pruritus using the I-NRS. At selected sites, the target lesion will be photographed and scored with the Signs of AD score.
 
If a subject discontinues from the study early, all Day 85 assessments will be completed.
 
After completion of study assessments, the subject will be discharged from the study.

Statistical Methods
	
All statistical processing will be performed using SAS[®] unless otherwise stated.
 
Analysis Sets:
 
This study will be evaluated using 3 analysis sets: intent-to-treat (ITT), per protocol (PP), and safety. Efficacy conclusions will be drawn from the ITT analysis set. The ITT analysis set will consist of all randomized subjects with at least one post-baseline efficacy assessment and will be based on randomized study group, regardless of study drug received. The PP analysis set will be used to support the efficacy findings in the ITT analyses and will include subjects with no major protocol deviations. Safety conclusions will be drawn from the safety analysis set. The safety analysis set will include all subjects that received at least one application of study drug and had at least one post-baseline safety assessment with treatment based on study drug received regardless of randomization group.
 
Demographics will be summarized using the safety analysis set by baseline age, gender, race, ethnicity, height, weight, and BMI. The primary efficacy analysis will be conducted on the ITT population. For continuous variables, the mean, standard deviation (SD), median, and range will be presented along with the 95% confidence interval (CI).

Categorical variables will be summarized by proportions along with the 95% CI.

Handling of Missing Data:

The primary method of handling missing efficacy data in the ITT analysis set will be based on LOCF. Other imputation methods (e.g., mixed model for repeated measurement [MMRM]) may be used as a sensitivity analysis.

All safety analyses will be conducted using the safety analysis set. No imputations will be made for missing safety data.

Efficacy Analyses:

The efficacy analyses will be performed using the ITT (primary) and PP (supportive) analysis sets. The efficacy variables include the IGA, BSA of AD, Signs of AD score, and EASI score collected at Screening and/or Baseline and all subsequent study visits. The primary efficacy endpoint for the study is the proportion of subjects with IGA success defined as an IGA score of Clear (0) or Almost Clear (1) with at least a 2-grade improvement from Baseline at Day 85. The IGA will be dichotomized into “success” and “failure” at study Day 15, Day 29, Day 57, and Day 85.

This Phase 2a study is designed to identify the response to BTX 1204 relative to vehicle. Statistical tests applied to the outcomes will be exploratory. No adjustments for Type 1 error will occur.

Success on IGA defined as a score of Clear (0) or Almost Clear (1) and at least a 2-grade improvement from Baseline at Day 15, Day 29, Day 57, and Day 85 will be analyzed using logistic regression, adjusting for Baseline IGA.

The change from Baseline in BSA of AD at Day 15, Day 29, Day 57 and Day 85 will be analyzed used ANCOVA with Baseline BSA of AD and treatment as covariates.

Summary statistics will be presented for the change from Baseline in each of the Signs of AD (erythema, exudation, excoriation, induration/papulation, and lichenification) at each timepoint (Day 15, Day 29, Day 57 and Day 85). A total score will be calculated based on the sum of each of the Signs of AD (0, 1, 2, or 3; max score of 15) and the change from Baseline will be summarized for each timepoint. The change from Baseline in Signs of AD at Day 15, Day 29, Day 57, and

	
Day 85 will be analyzed using ANCOVA with Baseline Signs of AD score and treatment as covariates.
 
Summary statistics will be prepared for the change from Baseline in the EASI Score and I-NRS at each timepoint (Day 15, Day 29, Day 57 and Day 85). Summary statistics will also be prepared for the change from Baseline in the Signs of AD score for the target lesion (selected sites) at each timepoint (Day 15, Day 29, Day 57 and Day 85).
 
Summaries of the pruritus scores reported by the subjects in the daily Patient Diary will be presented using daily means by treatment and with graphic presentations.
 
Safety Analyses:
 
All subjects who receive at least one confirmed dose of study drug and have at least one post-Baseline assessment will be included in the safety analyses. Safety analyses will include summaries of AEs, TEAEs, serious AEs (SAEs), and changes in laboratory assessments. AEs, TEAEs and SAEs will be coded using the MedDRA dictionary and summarized by treatment group, the number of subjects reporting events, system organ class, preferred term, severity, relationship to study drug, and seriousness. A list of subjects who prematurely discontinue from the study due to an AE and the reason for discontinuation will be provided.
 
The number and percentage of subjects reporting each medication will be summarized. Medications taken by each subject will be listed.
 
Changes in laboratory parameters from Baseline to Day 85 will be summarized using shift tables to evaluate for trends. Abnormal laboratory findings will be summarized and listed by subject.
 
Concomitant medications will be mapped to ATC Level 2 using the WHODrug dictionary. The number and percentage of subjects reporting each medication will be summarized. Medications taken by each subject will be listed.
 
Sample Size:
 
The sample size for this study is based on clinical considerations only. Subjects will be randomized 1:1 with 100 subjects in each treatment group for a total 200 subjects. This is considered adequate to evaluate the safety and tolerability and preliminary information on efficacy of

--	--

	twice daily BTX 1204 4% in the treatment of moderate atopic dermatitis in subjects aged 12-70.
--	--

SCHEMATIC OF STUDY DESIGN

[figure not shown]

TABLE OF CONTENTS

LIST OF ABBREVIATIONS.....	5
PROTOCOL SUMMARY.....	7
SCHEMATIC OF STUDY DESIGN.....	15
TABLE OF CONTENTS.....	16

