9.3.8. Handling of Missing Data

The primary method of handling missing efficacy data in the ITT analysis set will be based on LOCF. Other imputation methods (e.g., mixed model for repeated measurement [MMRM]) may be used as sensitivity analyses.

All safety analyses will be conducted using the safety analysis set. No imputations will be made for missing safety data.

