## **6. STATISTICAL AND ANALYTICAL PLANS**

### **6.1 General Methodology**

All statistical processing will be performed using SAS® 9.4 or higher. No interim analyses are planned. This Phase 2 study is designed to identify the response of BTX 1204 4.0% BID compared to Vehicle BID. Statistical tests will be exploratory. No adjustments for Type I error will occur.

Descriptive statistics will be used to provide an overview of the efficacy and safety results. For categorical parameters, the number and percentage of subjects in each category will be presented. For continuous parameters, descriptive statistics will include n (number of subjects), mean, standard deviation (SD), median, minimum and maximum.

The primary method of handling missing efficacy data in the Intent-to-Treat (ITT) and modified Intent-to-Treat (mITT) analysis sets will be based on last observation carried forward (LOCF). Repeated measures analyses will be used on the observed data as a sensitivity analysis on the primary endpoint.

The efficacy analysis performed on the ITT population is considered the primary analysis. The efficacy analyses performed on the mITT and per-protocol (PP) populations are considered supportive analyses.

The number of subjects in each analysis set will be summarized. Reasons for study withdrawal during the study will be summarized using frequencies and percentages by treatment group.

Reported AEs, medical history terms and prior and concomitant procedures and therapies will be classified on the basis of Medical Dictionary for Regulatory Activities (MedDRA) terminology. Prior and concomitant medications will be classified on the basis of World Health Organization Drug Dictionary (WHO-DDE) terminology.

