#### **6.1.5 Handling of Dropouts or Missing Data**

All efforts will be made to minimize the occurrence of missing data. It is not expected that dropout rates will differ between groups. Therefore, the primary method of handling missing efficacy data in the ITT and mITT analysis set will be based on LOCF. Summary of efficacy variables for the PP subjects will be based on available data. No imputation will be done for non-efficacy related variables.

If a partial date is reported where the day is missing, then the day will be imputed as the first day of the month unless the month is the same month as the first application of study drug then the day will be that of first application with the month and year remaining the same. If a partial date is reported where the month is missing, then the month will be imputed to January unless the year is the same year as the first application of study drug then the month will be that of first application with the year remaining the same. If a partial date where both the day and month is missing, follow details as stated previously.

Missing AE start dates will be imputed using partial date imputation rules as previously described in this Section.

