## **6.8.2 Secondary Efficacy Analysis**

### **6.8.2.1 Signs of Atopic Dermatitis at Day 85**

The Signs of AD total score will be calculated based on the sum of the score for each component (erythema, exudation, excoriation, induration/papulation, and lichenification). Each component will be scored as 0, 1, 2, or 3. The total score therefore ranges from 0 to a maximum score of 15.

The change from Baseline to Day 85 in the total Signs of AD score will be analyzed using analysis of covariance (ANCOVA) with Baseline Signs of AD as covariate and treatment as a factor.

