#### **6.10.1 Repeated Measures**

The first sensitivity analysis for the primary endpoint, IGA success, will be analyzed using a repeated measures logistic regression (generalized estimating equations), with dichotomized IGA success as the dependent variable and treatment group, visit, and treatment group by visit interaction as independent factors. In this analysis, data from all post-Baseline visits will be included with no imputation for missing data.

```
proc genmod data = datain;
  class SUBJECT TRT VISIT;
  model IGA SUCCESS = TRT VISIT TRT * VISIT / dist=bin;
  repeated subject = SUBJECT/type = cs;
  lsmeans TRT*VISIT / diff;
  estimate 'pval' TRT 1 -1 TRT*VISIT 0 0 1 0 0 -1;
run;
```

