Table 14.3.1.2: Summary of Treatment-Emergent Adverse Event by MedDRA System Organ Class and Preferred Term (Safety Population).....	94
Table 14.3.1.3: Summary of Serious Treatment-Emergent Adverse Events by MedDRA System Organ Class and Preferred Term (Safety Population).....	95
Table 14.3.1.4: Summary of Related Treatment-Emergent Adverse Events by MedDRA System Organ Class and Preferred Term (Safety Population).....	95
Table 14.3.1.5: Summary of Severe Treatment-Emergent Adverse Events by MedDRA System Organ Class and Preferred Term (Safety Population).....	95
Table 14.3.1.6: Summary of Treatment-Emergent Adverse Events Leading to Study Discontinuation by MedDRA System Organ Class and Preferred Term (Safety Population).....	95
Table 14.3.1.7: Summary of Time to Study Discontinuation for Subjects Who Discontinue Due to Treatment-Emergent Adverse Events (ITT Population).....	96
Table 14.3.1.8: Summary of Treatment-Emergent Abuse-Related Adverse Events by MedDRA System Organ Class and Preferred Term (Safety Population).....	97
Table 14.3.2.1.1: Summary of Chemistry Results by Visit (Safety Population) .....	98
Table 14.3.2.1.2: Shift Table for Chemistry Results (Safety Population) .....	99
Table 14.3.2.2.1: Summary of CBC Results by Visit (Safety Population).....	100
Table 14.3.2.2.2: Shift Table for CBC Results (Safety Population).....	100
Table 14.3.2.3.1: Summary of Numeric Urinalysis Results by Visit (Safety Population) .....	100
Table 14.3.2.3.2: Shift Table for Numeric Urinalysis Results (Safety Population) .....	100
Table 14.3.2.3.3: Summary of Character Urinalysis Results by Visit (Safety Population).....	101

Table 14.0.1: Summary of Subject Completion/Discontinuation  
(Randomized Subjects)

	BTX 1204 4% BID (N=xxx)	Vehicle BID (N=xxx)
Completed Study		
Yes	xx ( xx.x%)	xx ( xx.x%)
No	xx ( xx.x%)	xx ( xx.x%)
Reason for Discontinuation from Study		
Adverse Event	xx ( xx.x%)	xx ( xx.x%)
Death	xx ( xx.x%)	xx ( xx.x%)
Lost to Follow-Up	xx ( xx.x%)	xx ( xx.x%)
Physician Decision	xx ( xx.x%)	xx ( xx.x%)
Pregnancy	xx ( xx.x%)	xx ( xx.x%)
Protocol Violation	xx ( xx.x%)	xx ( xx.x%)
Study Terminated by Sponsor	xx ( xx.x%)	xx ( xx.x%)
Withdrawal by Subject	xx ( xx.x%)	xx ( xx.x%)
Worsening Condition	xx ( xx.x%)	xx ( xx.x%)
Other		

SOURCE: USERNAME\SPONSOR\PROJECT\JOBNAME (DATE,TIME)

Table 14.0.2: Summary of Subjects Excluded from Analyses  
(Randomized Subjects)  
(Page 1 of 2)

	BTX 1204 4% BID (N=xxx)	Vehicle BID (N=xxx)

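### In ITT, no planned analysis checks LOCF for Signs of AD or %BSA; an MMRM on observed data, which the protocol already permits, would do so

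*Protocol*

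**What the plan says.** **Protocol.** LOCF is the primary method for missing efficacy data in ITT. Beyond it, the Protocol Summary says only: "Other imputation methods (e.g., mixed model for repeated measurement [MMRM]) may be used as a sensitivity analysis". Section 9.3.8 says the same, and neither place ties MMRM to an endpoint.

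**SAP, primary handling.** Section 6.1.5 states that "the primary method of handling missing efficacy data in the ITT and mITT analysis set will be based on LOCF". It reaches this from the expectation that the two arms will drop out at similar rates. For the per-protocol set the rule is different: "Summary of efficacy variables for the PP subjects will be based on available data".

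**SAP, continuous secondary endpoints.** Sections 6.8.2.1 and 6.8.2.4 analyse Day 85 change in Signs of AD and in %BSA by ANCOVA on baseline and treatment. The ITT shells (Tables 14.2.2.1.1 and 14.2.2.3.1) carry an LOCF footnote, which is replaced by a no-imputation footnote only in the per-protocol repeats. I-NRS, the third continuous secondary endpoint, is summarised without a test.

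**SAP, sensitivity analyses.** Section 6.1 limits the observed-data model to one endpoint: "Repeated measures analyses will be used on the observed data as a sensitivity analysis on the primary endpoint". Section 6.10.1 specifies it as a logistic GEE: "In this analysis, data from all post-Baseline visits will be included with no imputation for missing data". Section 6.10.2 adds a tipping-point analysis, again for IGA success only.

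**The concern.** The step from similar dropout rates to LOCF does not follow. LOCF gives each early leaver their last score as if it were the Day 85 score. If the treatment effect is still growing between visits, this shrinks the Day 85 difference even when both arms lose the same fraction for reasons unrelated to outcome. If leaving depends on response and does so differently by arm, the error can go either way. Response-related exit is plausible here: Table 14.0.1 lists "Worsening Condition" among the reasons for discontinuation.

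For IGA success, the GEE and the tipping point give the reader something to set beside the LOCF result. For Signs of AD and %BSA, nothing in ITT does. Signs of AD is the scale on which the Phase 1b signal was reported (Protocol 1.3.2: 34.8% against 18.2% with an improvement of at least 4 points), and the protocol says this trial will guide later studies. Both scales are scored at all four post-Baseline visits, so the data for a better check will already exist.

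**Working it through.** The plan states no dropout rate, SD, effect size or power, so there is no figure to reproduce. All inputs below except the visit schedule are assumptions.

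**1. Coverage of the planned analyses.**

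| Analysis | Set | IGA success | Signs of AD, %BSA |
|---|---|---|---|
| Primary model, LOCF | ITT, mITT | yes | yes |
| GEE, observed data | ITT | yes | no |
| Tipping point | ITT | yes | no |
| No imputation | PP | yes | yes |

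SAP 6.4.5 removes subjects without a Day 85 IGA from PP. It readmits those who stopped for a related AE or documented lack of effect. A readmitted subject with no score mapped to Day 85 still adds nothing to an unimputed Day 85 ANCOVA.

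**2. Equal, outcome-unrelated dropout, by hand.** Assume treatment differences of -0.05, -0.15, -0.30 and -0.40 SD at Days 15, 29, 57 and 85, and a chance *h* of leaving after each of the first three visits, the same in both arms. Then

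LOCF difference = Σ P(last visit = v) × difference at v, with probabilities h, h(1-h), h(1-h)², (1-h)³.

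- h = 0.10: probabilities 0.100, 0.090, 0.081, 0.729 (27% missing at Day 85). LOCF = -0.0050 - 0.0135 - 0.0243 - 0.2916 = -0.334. Shortfall: 1 - 0.334/0.400 = 16%.
- h = 0.04: probabilities 0.040, 0.038, 0.037, 0.885 (11.5% missing). LOCF = -0.373. Shortfall: 7%.

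The rates are identical and the missingness is harmless, yet LOCF is biased because the effect is still growing.

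**3. Response-dependent dropout, same mean profile.** Simulation of 200,000 per arm; mean change -0.30, -0.60, -0.90, -1.10 (active) and -0.25, -0.45, -0.60, -0.70 (vehicle); variance 1; correlation 0.4 + 0.6 × 0.7^lag. The simulated true difference is -0.396.

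| Chance of leaving per interval | Missing at Day 85, active / vehicle | LOCF | MMRM |
|---|---|---|---|
| 15% if last change is above -0.3, else 3%; both arms | 20% / 22% | -0.348 | -0.395 |
| Active flat 8%; vehicle 25% if above -0.3, else 3% | 22% / 32% | -0.442 | -0.394 |

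LOCF is 12% too small (0.348/0.396 = 0.88), then 12% too large (0.442/0.396 = 1.12).

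**4. Signs scale, assumed true difference -1.4 points.**

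| Dropout | LOCF | Error relative to 1.4 |
|---|---|---|
| about 12%, balanced | -1.36 | 0.04/1.4 = 3% too small |
| 22 to 25%, balanced | -1.28 | 0.12/1.4 = 9% too small |
| unbalanced | -1.05 to -1.82 | 25% too small to 30% too large |
| unbalanced, half of earlier leavers with an exit score | -1.11 to -1.69 | 21% either way |

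The likelihood (MMRM) estimate stayed within about 0.01 of the truth. A separate run at about 10% dropout in both arms gave LOCF -1.34 to -1.37, or 2 to 4% too small. The larger percentages in steps 2 and 3 come from a different assumed growth of effect, so the size depends on the trajectory as well as on dropout.

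**5. The contrast in SAP 6.10.1.** Two arms and four post-Baseline visits make eight treatment-by-visit cells, but the ESTIMATE statement gives six interaction coefficients. With treatment varying slowest, the third coefficient is the first arm's third visit (Day 57) and the sixth is the second arm's second visit (Day 29). Such a contrast also needs visit main-effect coefficients, which are absent. A rank check confirms that it is estimable with three visits and not with four.

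**The case against.** **The protocol only permits MMRM.** True. A reader might infer that the SAP abandoned a commitment and failed to declare this in Section 8. The wording is permissive and MMRM is given as an example, so no commitment was broken and Section 8 omits no change on this account.

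**Other outputs would give a warning.** A reader might conclude that nothing planned could expose a problem. That goes too far: a gap between ITT and PP results, or unequal discontinuation in Table 14.0.1, could raise suspicion. Neither estimates the Day 85 ITT difference without LOCF.

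**Exit assessments help.** The protocol asks for Day 85 assessments at early exit, with attempts or where possible in sections 6.3.8 and Table 4, and SAP 6.1.3 maps them to visit windows. An exit on study days 71 to 98 counts as Day 85 if no scheduled value is present. This reduces the bias, as step 4 shows, but does not remove it.

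**The trial is exploratory.** Tests are unadjusted and the sample size has no power basis. An argument from lost power would therefore measure against a target the trial does not have. The bias in the estimate remains relevant.

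**The simulations favour MMRM.** They do: dropout depended on observed scores, which is what MMRM assumes. It is proposed as a second view and not as proof of the true value.

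**The GEE.** A reader might also want it weighted, since an unweighted GEE needs dropout unrelated to earlier IGA. With an assumed true difference of 11.8 points, its error was 0.3 to 0.5 points when the mechanism was the same in both arms, and at most 2.7 (9.1 against 11.8) when mechanisms were opposed. The tipping point already probes arm-specific missingness, and no benefit from weighting has been shown.

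**Conclusion.** The gap is real and limited to the continuous endpoints: for Signs of AD and %BSA, no planned ITT analysis tests the LOCF result. The SAP's reason for LOCF does not protect it when the effect changes over visits or when leaving depends on response.

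On the Signs scale assumptions, the error is about 3 to 4% of the effect at roughly 12% balanced dropout, 8 to 9% at 22 to 25%, and up to about 30% in either direction when dropout is unbalanced. It is smaller where exit scores are obtained, and larger at balanced dropout if more of the effect arrives late (7% at 11.5% and 16% at 27% in the hand calculation). Every one of these figures rests on assumed dropout, variance and trajectory.

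This is a worthwhile improvement and not a deviation from the protocol. It gives no ground for replacing LOCF as the primary method or for weighting the GEE. Separately, the ESTIMATE statement in 6.10.1 is a plain coding error.

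**What to change.** - **SAP 6.10:** keep the LOCF ANCOVA as the primary method. Add an MMRM on observed ITT data for change in Signs of AD total score and change in %BSA, with treatment, visit, treatment-by-visit, baseline and baseline-by-visit, and unstructured covariance. Report the Day 85 treatment difference with its 95% CI beside the ANCOVA result.
- **SAP 6.10.1:** rewrite the interaction part of the ESTIMATE statement with eight coefficients. With visits sorted Day 15, 29, 57, 85 this is `TRT 1 -1 TRT*VISIT 0 0 0 1 0 0 0 -1`. Alternatively, take the Day 85 comparison from the LSMEANS difference already requested.
- **Timing:** make both changes before unblinding.

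The cost is SAP text and a few tables, with no new data. The drawback is a second result per continuous endpoint, so the SAP should say in advance that the LOCF ANCOVA stays primary and the MMRM is read as a check on it.
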